8 PHARMACOKINETICS

A listing of the pharmacokinetic collection times will be provided, but the analyses will be described in a separate report.

9 SAFETY ANALYSIS

All safety analyses will be performed in the Safety Population. The results in the DB and OL phases will be summarized separately. In both phases, the results will be summarized by the DB treatment actually received and, for the OL phase of the study, combined over the treatment groups. Baseline for safety endpoints is defined as the last non-missing value obtained before the first day of DB treatment. Assessments performed at multiple post-baseline time points will be summarized at each time point for which they are scheduled, but the listings will also include any assessments performed at unscheduled time points.

The number and percentage of days that subjects received investigational product, the highest percentage of the maximum allowable daily dose (1800 mg or 63 mg/kg) that subjects received, and the total amount of investigational product received will be summarized. For the OL phase, they will be summarized over just the OL phase as well as over the entire study (combined DB and OL phases) but the classification by the DB treatment applies only for the OL phase summary. The summarization over the entire study will include only subjects who were in the GNX group during the DB phase, regardless of whether they entered the OL, and all the subjects from the OL phase. A subject data listing will be provided with full details of the study drug dispensation.

Safety assessments include:

- AEs
- Clinical laboratory tests
- Vital signs including BP, HR, RR, body temperature, weight, and height
- 12-lead Electrocardiogram (ECG)
- Physical, neurological and developmental examinations
- Neurosteroid levels
- Tanner staging (OL phase only)

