7.6. Safety Assessments

Safety will be evaluated by collecting the assessments detailed in the sections below.

Baseline is defined as the last non-missing value obtained before the first DB treatment. If any of the baseline safety assessments are outside of normal limits, and the investigator feels is medically significant, the subject may not be randomized. Assessments performed at multiple post-baseline time points will be summarized at each time point for which they are scheduled, but the listings will also include any assessments performed at unscheduled time points.

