7.6.4. ECG

Electrocardiograms will be performed to collect the electrical activity of the heart throughout the study to monitor safety. An evaluation of normal by a physician must be obtained before the subject is randomized to the DB phase.

ECGs will be performed as follows:

- DB phase:
 - Visit 2 (baseline/randomization)
 - Visit 3 (Week 5)
 - Visit 5 (Week 17 = Final DB Visit/First OL phase visit)

- OL phase:
 - Visit 6 (Week 21)
 - Visit 8 (Week 52 and then yearly)
 - Final OL Visit

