9.7. General Statistical Considerations

Source data for the summary tables and statistical analyses will be presented as subject data listings, which include data collected on the electronic case report forms (eCRFs) as well as any derived efficacy variables for all enrolled subjects.

Except where noted, separate tables and data listings will be prepared for the DB and OL phases of the study. Only events occurring before entry into the OL phase will be included in the DB phase outputs, and except where indicated, only baseline events and events occurring after entry into the OL phase will be included in the OL phase outputs.

Baseline seizure activity will be determined by prospective recording in subject's daily seizure eDiaries, which are provided after signing informed consent/assent. Within the DB phase of the study, determination of post-baseline seizure activity will begin on the day following the first day

of DB treatment. Determination of post-baseline seizure activity assigned to the OL phase will begin on the day following the first OL treatment.

Tables will be provided using the ITT subject population as well as within each of the biomarker-positive and biomarker-negative strata. The within-stratum PBO group will consist of only the subjects within the corresponding stratum. The tables for the DB phase will show the results for each DB treatment group and, where noted, combined over the groups as well. The tables for the OL phase will show the results for each DB treatment group (all subjects will be receiving GNX in the OL phase) and combined over them. For the efficacy endpoints, the results will be derived according to the randomized treatment group; for the other endpoints, they will be derived according to the treatment actually received.

Baselines for non-seizure efficacy and safety assessments are defined as the last non-missing value of the assessment before the first dose of treatment.

The OL phase will use the same baseline as the DB phase.

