Baseline seizure activity will be determined by the subject's daily seizure eDiary entries for the 8 or 12 week period immediately prior to Visit 2 (Day 0), depending on eligibility criteria in the applicable protocol version. For primary seizures only, if a subject's baseline seizure count from this prospective baseline period is less than 4, the primary seizure count from the Historical Seizure Calendar Review CRF will be used to calculate a baseline 28-day seizure count. Within the DB phase of the study, determination of post-baseline seizure activity will begin on the day following the first day of DB treatment. The first day of DB treatment (Day 0) is included in neither the baseline nor DB phase since seizures could occur both before and after the initiation of treatment. Determination of post-baseline seizure activity assigned to the OL phase will begin on the day following the first OL treatment.

Baseline values for non-seizure efficacy and safety assessments are defined as the last non-missing value of the assessment before the first dose of treatment.

The OL phase will use the same baseline as the DB phase.

The study day for all assessments that are performed on or after the first day of treatment will be calculated as:

$$\text{Study Day} = \text{date of the assessment} - \text{date of first treatment} + 1.$$

For assessments performed before the first day of treatment, the study day calculation is:

$$\text{Study day} = \text{date of the assessment} - \text{date of first treatment}.$$

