14.3.2 Potentially Clinically Significant ECG Criteria

HR:

See criteria in Vital Signs

PR interval:

< 0.9 x LLN or >1.1 x ULN

QRS:

>1.1 x ULN

QTc B/FN interval:

≥ 470 msec (females)

or increase ≥ 60 msec from baseline (note. QTc is not changing with age)

QT Prolongation analysis uses the reported, corrected QT interval from the study data, and it also computes corrected QTc intervals using the following three industry-standard formulas, which are the same except for the correction factor applied to the RR interval:

- QTcB is the length of the QT interval corrected for the RR interval by Bazett's formula: $QTcB = QTmsec / (RR \text{ sec})^{0.5}$
- QTcN is the length of the QT interval corrected for the RR interval by FDA Neuropharmacological Division's formula: $QTcN = QTmsec / (RR \text{ sec})^{0.37}$
- QTcF is the length of the QT interval corrected for the RR interval by Fridericia's formula: $QTcF = QTmsec / (RR \text{ sec})^{0.33}$

PR, QRS Normal Ranges:

Age	PR Interval (sec) [*]	QRS Duration (sec) [†]
1–3 yr	0.10–0.14	<= 0.07
4–5 yr	0.11–0.15	<= 0.08
6–8 yr	0.12–0.16	<= 0.08
9–11 yr	0.12–0.17	<= 0.09
12–16 yr	0.12–0.17	<= 0.10
>16 yr	0.12–0.20	<= 0.10

14.3.3 Potentially Clinically Significant Vital Signs ValuesHR:

High: $1.20 \times \text{ULN}$; or an ≥ 15 bpm increase from baseline if clinically significant at baseline

Low: $0.80 \times \text{LLN}$; or an ≥ 15 bpm decrease from baseline if clinically significant at baseline

Systolic BP:

High: $1.5 \times \text{ULN}$; or an ≥ 20 increase from baseline if clinically significant at baseline

Low: $0.75 \times \text{LLN}$; or an ≥ 20 decrease from baseline if clinically significant at baseline

Diastolic BP:

High: $1.3 \times \text{ULN}$; or an ≥ 15 increase from baseline if clinically significant at baseline

Low: $0.70 \times \text{LLN}$; or an ≥ 15 decrease from baseline if clinically significant at baseline

Respiratory Rate

Low: 0.80 x LLN

High 1.25 x ULN

Vital Signs Normal Ranges by Age

Age	HR (beats/min)	BP (mm Hg)	RR (breaths /min)
1 – 3 yrs	80 - 125	90 – 105 / 55 - 70	20 - 30
3 – 6 yrs	70 - 115	95 – 110 / 60 - 75	20 - 25
6 – 12 yrs	60 – 100	100 – 120 / 60 – 75	14 - 22
>12 yrs	60 – 100	100 – 120 / 70 – 80	12 - 18

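### SAP 9 sets the safety baseline before the first treatment day, contradicting SAP 2.1 and the protocol; if followed, a subject dosed on the Visit 2 date has no scheduled ECG baseline

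*SAP*

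**What the plan says.** Four places define the safety baseline.

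- SAP 9: "Baseline for safety endpoints is defined as the last non-missing value obtained before the first day of DB treatment".
- SAP 2.1: "Baseline values for non-seizure efficacy and safety assessments are defined as the last non-missing value of the assessment before the first dose of treatment".
- Protocol 9.7: "Baselines for non-seizure efficacy and safety assessments are defined as the last non-missing value of the assessment before the first dose of treatment".
- Protocol 7.6: "Baseline is defined as the last non-missing value obtained before the first DB treatment".

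SAP 2.1 also attaches the label Day 0 both to Visit 2 and to the first treatment day. For seizures it adds: "The first day of DB treatment (Day 0) is included in neither the baseline nor DB phase". SAP 11 declares no major change in the planned analyses and describes the SAP as consistent with the current protocol.

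ECGs in the double-blind phase are scheduled at Visits 2, 3 and 5 (Protocol 7.6.4, Protocol Table 1, SAP 14.1.1). None is scheduled at screening. SAP 9.3.2 calls for ECG change from baseline by visit. One arm of the QTc criterion in SAP 14.3.2 reads "or increase ≥ 60 msec from baseline".

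**The concern.** In this SAP, day and dose are different cut-offs. SAP 2.1 drops the whole first treatment day from the seizure phases because a seizure on that day may fall on either side of the first dose. Its next paragraph sets the non-seizure and safety baseline at the first dose. SAP 9 then applies the day cut-off to safety data, where the reason for it does not carry over: Visit 2 safety assessments are meant to be done before dosing.

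SAP 9 introduces all the safety outputs, and the SAP gives no rule on which section prevails. Two programmers, one working from SAP 9 and one from SAP 2.1, could therefore build different baselines from the same data. At stake are the ECG change table, the QTc-increase flag, the laboratory changes and shift tables (SAP 9.2) and the vital-sign changes (SAP 9.3.1).

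**Working it through.** The plan states no figure to reproduce. The check applies each rule to the schedule of assessments.

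**Step 1: when do the rules differ?** Let V be the Visit 2 date and D the date of first dose, with D on or after V.

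- Cut-off at first dose (SAP 2.1, Protocol 9.7; Protocol 7.6 in substance): a Visit 2 value taken pre-dose is baseline whether D = V or D > V.
- Cut-off at first day (SAP 9): a value dated V qualifies only if V < D. If D = V, it is excluded.

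The rules therefore differ only when D = V. That is the nominal case in SAP 2.1, where both are Day 0.

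**Step 2: what baseline does a subject with D = V get?**

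| Assessment | Scheduled pre-dose | Baseline under first-dose rule | Baseline under SAP 9 |
|---|---|---|---|
| ECG | Visit 2 only | Visit 2 | none scheduled |
| Chemistry, hematology | Screening, Visit 2 | Visit 2 | Screening |
| Vital signs, weight | Screening, Visit 2 | Visit 2 | Screening |
| Physical, neurological, developmental examination | Screening, Visit 2 | Visit 2 | Screening |
| Urinalysis | Screening, or Visit 2 if not obtained then | whichever is available | Screening, or none if first collected at Visit 2 |
| Height, Tanner stage, neurosteroids | Screening only | Screening | Screening |

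**Step 3: how far back does the baseline move?** Protocol 7.2.1.3 allows 84 to 90 days between screening and randomization (12 × 7 = 84; 84 + 6 = 90). SAP 2.1 and 7.1 also cover subjects with an 8-week baseline under earlier protocol versions, for whom the gap is about 8 × 7 = 56 days.

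**Step 4: which outputs fail and which only shift?** For a subject with D = V under SAP 9, ECG change from baseline and the QTc increase of at least 60 msec cannot be derived. The other QTc arm, an absolute value of at least 470 msec, needs no baseline and is unaffected. Laboratory and vital-sign changes can still be calculated, but from the screening value.

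**Step 5: is the day numbering consistent?** For dates on or after first treatment, SAP 2.1 defines Study Day as assessment date minus first treatment date plus 1. On the first treatment day this gives 0 + 1 = 1. The day before gives −1. The formula never produces a Day 0, yet the same section calls the first treatment day Day 0.

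**The case against.** The strongest reply is that a usable rule already exists. SAP 2.1 names safety assessments explicitly, Protocol 9.7 repeats it and Protocol 7.6 agrees in substance. The schedule itself calls Visit 2 the baseline visit, and SAP 11 declares no departure from the protocol. This stands. The defect is a contradiction, and the intended answer is clear. A reader might infer from SAP 9 that the trial has no ECG baseline at all. The documents do not support that, because the inference requires SAP 9 to override the other three statements.

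A second reply is that dosing on the Visit 2 date is not fixed. Protocol 7.2.1.3 requires procedures to be complete and results received before investigational product is given. The list includes chemistry, a plasma drug screen and a serum pregnancy test, and it ends with dispensing, without saying that the first dose is taken that day. This also stands. A reader might infer that all of the approximately 25 randomized subjects are affected, but the documents do not show how many took their first dose on the Visit 2 date.

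A third tempting inference is that every other baseline moves back by at least 84 days. That fails too. Some subjects had an 8-week baseline, some assessments are taken only at screening under either rule, and a late urinalysis is lost, not moved.

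None of this removes the conflict. SAP 9 is a stated rule that gives a wrong result when applied literally to a subject dosed on the Visit 2 date. If dosing dates vary, it also gives some subjects a Visit 2 baseline and others a screening baseline in the same table.

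**Conclusion.** The SAP contains two conflicting safety baseline rules, and the one in SAP 9 is wrong as written. The consequences rest on two conditions: SAP 9 is the rule followed, and the first dose falls on the Visit 2 date. Where both hold, the subject loses her scheduled ECG baseline and several other baselines move back to screening. Where either fails, nothing changes. The number of subjects concerned cannot be determined from the documents.

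The effect is confined to descriptive safety summaries and potentially-clinically-significant flags. SAP 9 governs safety endpoints only. The seizure baseline has its own rule, and the non-seizure efficacy baseline stays with SAP 2.1, so no efficacy test is affected. The correction should still be made, because as it stands the SAP does not determine which safety tables will be produced.

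**What to change.** 1. In SAP 9, change the cut-off from the first day to the first dose of double-blind treatment, matching SAP 2.1 and Protocol 9.7 and agreeing with Protocol 7.6.
2. State that Visit 2 assessments are baseline when taken pre-dose, and that those recorded on the dosing date without a time are treated as pre-dose. This follows the order of events in Protocol 7.2.1.3.
3. In SAP 2.1, reconcile the Day 0 label with the Study Day formula, which makes the first treatment day Day 1.

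The cost is one changed word, a clarifying sentence and a labelling correction in the SAP. It needs no new data and no change to any test.

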9.1 ADVERSE EVENTS

AEs will be coded by System Organ Class (SOC) and Preferred Term (PT) using MedDRA®, version 22.0 or higher. The verbatim term will be included in the AE listings. Except where indicated, the summary tables will include only treatment-emergent adverse events (TEAEs). All AEs, treatment-emergent or otherwise, will be

presented in subject data listings.

A TEAE is defined as an AE that starts or worsens on or after the first dosing day of study drug. The AE analyses for the DB treatment phase of the study will include AEs that start or worsen during that phase and will not include AEs that start or worsen during the OL phase; i.e., they will not include any AEs starting or worsening on or after the first dosing day of the OL phase.

For the OL phase of the study, the adverse event results will be summarized over just the OL phase as well as over the entire study (DB and OL phases) but the classification by the DB treatment applies only for the OL phase summary. The summarization over the entire study will include only subjects who were in the GNX group during the DB phase, regardless of whether they entered the OL, and all the subjects from the OL phase; i.e., it will include only the TEAEs following GNX exposure. The summarizations over just the OL phase will include TEAEs that occur or worsen on or after the first day of the OL phase; the summarizations over the entire study will include TEAEs that start or worsen on or after the first dosing day of GNX.

The TEAEs will be summarized as the number of events and the number and percentage of subjects with TEAEs. Subjects who report the same PT on multiple occasions will be counted once for the PT: under the highest severity (severe > moderate > mild) when summarized by severity and under the closest relationship (related > not related) to study drug when summarized by relationship.

If a subject reports multiple PTs for a SOC, the subject will be counted only once for that SOC. For the counting of events, all the PTs will be included in the counts, even when subjects have multiple PTs.

Non-treatment emergent AEs will only be listed.

TEAEs will be summarized as follows:

- An overview table of TEAEs, including number of events and number (%) of subjects with:
 - TEAEs
 - Serious AEs (SAEs)
 - Study drug related TEAEs
 - TEAEs by severity
 - TEAEs leading to study discontinuation
 - TEAEs leading to death
 - Adverse events of special interest (AESI)
- TEAEs by SOC and PT

- TEAE by SOC, PT, and Severity
- Study drug related TEAEs by SOC, PT
- SAEs by SOC and PT
- TEAEs leading to study drug discontinuation by SOC and PT
- TEAEs leading to dose reduction by SOC and PT
- Adverse events of special interest (AESI)

All AE tables will be sorted by SOC and PT in decreasing frequency of the number of subjects in the GNX group, in the DB summaries and the combined groups in the OL summaries; in case of tied frequencies, the sorting will be alphabetical.

Adverse event listing will identify serious AEs, AE leading to study drug discontinuation, AEs leading to dose reduction, AEs of special interest, and subjects who died during the study.

For purposes of determining treatment emergence, missing start dates will be imputed as shown in Table 3; however, the actual dates, not the imputed ones, will be displayed in the data listing.

Table 3: Handling of Partial or Missing Adverse Event Dates

Partial Missing Start or Stop Date	Imputed Start Date	Imputed Stop Date
Missing month, day, and year	First dose date	
Missing month and day, and the year is present	First dose date if the year is the same as the year of first dose date, else first dose date of the OL if the year is the same as the year of the first OL dose date, else January 1 of the AE start year.	December 31 of that year
Missing day, but year and month are present	First dose date if the year and month are the same as the year and month of first dose date, else first dose date of the OL if the year and month are the same as the year and month of the first OL dose date, else the 1 st of the AE start month.	Last day of that month
Missing month, but year and day are present	Assume day is also missing and impute as above	Missing month imputed as December

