7.2.1.3. Baseline Visit – Randomization (Visit 2, Week 0 + 6 days)

The following study procedures/assessments to be completed, the results received, and the investigator must ensure the subject meets all inclusion and exclusion criteria prior to IP administration. The 12 weeks between Screening and Randomization can be no less than 84 days and no more than 90 days.

- Review of inclusion/exclusion criteria
- Demographics and medical history review
- SIF/DRF (Epilepsy Study Consortium) approval
- Vital signs (to include BP, HR, RR, body temperature, and weight)
- Physical, neurological, and developmental follow-up examination
- ECG
- Clinical laboratory tests (to include CBC with automated differential, creatinine, blood urea nitrogen, and comprehensive metabolic panel)
- Urinalysis (If the urine sample was not collected at screening, it must be collected at baseline in order to complete the study-related procedures per protocol)
- Drug screen (plasma)
- Serum pregnancy test for females of childbearing potential
- Concomitant AED review and levels if per SOC
- Adverse events
- Seizure and medication diary review
- CSHQ
- BRIEF
- ABC-C
- EEG
- PedsQL-FIM
- QI-Disability
- CGI-C (parent/caregiver/LAR identified behavioral target)
- CGI-I (parent/caregiver/LAR and clinician)
- Dispense IP

7.2.2. Double-Blind Titration + Maintenance (3 Days, Weeks 1 to 4, 5, 9, 11, and 13)

7.2.2.1. Telephone Follow-up (Day 3 ± 1 Day and Weeks 1, 2, 3, and 4 ± 3 days)

A telephone follow-up visit will be conducted at Day 3 and Weeks 1, 2, 3, and 4 to assess the following:

- Adverse events
- Seizure and medication diary review

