8. ADVERSE AND SERIOUS ADVERSE EVENT ASSESSMENTS

8.1. Definition of Adverse Events, Period of Observation, Recording of Adverse Events

An AE is any untoward medical occurrence in a clinical investigation subject who has been administered a pharmaceutical product; it does not necessarily have a causal relationship with this treatment. An AE can therefore be any unfavorable and unintended sign (including an abnormal laboratory finding), symptom, or disease temporally associated with the use of a medicinal (investigational) product, whether or not related to the medicinal (investigational) product (International Conference on Harmonisation [ICH] Guidance E2A March 1995).

All AEs are collected from the time the informed consent (and subject assent) is signed until the defined follow-up period. This includes events occurring during the screening phase of the study, regardless of whether or not the IP has been administered. All AEs reported after the initiation of IP will be considered treatment-emergent AEs. Where possible, a diagnosis rather than a list of symptoms should be recorded. If a diagnosis has not been made, then each symptom should be listed individually. All AEs should be captured on the appropriate AE pages in the eCRF and in source documents. In addition to untoward AEs, unexpected benefits outside the IP indication should also be captured on the AE eCRF page.

All AEs must be followed to closure (the subject's health has returned to baseline status or all variables have returned to normal), regardless of whether the subject is still participating in the study. Closure indicates that an outcome is reached, stabilization is achieved (the PI does not expect any further improvement or worsening of the event), or the event is otherwise explained. When appropriate, medical tests and examinations are performed so that resolution of event(s) can be documented.

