Table 2: Handling of Partial or Missing Medication Dates

Partial Missing Start or Stop Date	Imputed Start Date	Imputed Stop Date
Missing year, month, and day	First dose date	
Missing month and day, and the year is present	First dose date if the year is the same as the year of first dose date, else first dose date of the OL if the year is the same as the year of the first OL dose date, else January 1 of the start year.	December 31 of that year
Missing day, but year and month are present	First dose date if the year and month are the same as the year and month of first dose date, else first dose date of the OL if the year and month are the same as the year and month of the first OL dose date, else the 1st of the start month.	Last day of that month
Missing month, but year and day are present	Assume day is also missing and impute as above	Missing month imputed as December

If an imputed start date is later than the stop date, then the stop date (after any needed imputations) will be used instead for the imputed start date.

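### SAP Table 3 has no stop-date check, so an adverse event recorded as over before the first dose can be counted as treatment-emergent when its start date is missing or matches the first-dose year or month

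*SAP*

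**What the plan says.** **Definition.** SAP Section 9.1: "A TEAE is defined as an AE that starts or worsens on or after the first dosing day of study drug". The stop date plays no part. Events that are not treatment-emergent appear in listings only, so this classification decides what reaches the summary tables.

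**Imputation.** The same section says "For purposes of determining treatment emergence, missing start dates will be imputed as shown in Table 3". Table 3 gives the first dose date in three situations:

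- the start is wholly missing (row "Missing month, day, and year");
- only the year is known: "First dose date if the year is the same as the year of first dose date";
- only the day is missing: "First dose date if the year and month are the same as the year and month of first dose date".

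If the known part does not match the first dose, it is compared with the first open-label dose. Failing that too, the start becomes 1 January of the year or the first of the month.

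**The medication counterpart.** Table 2 in SAP Section 6 has the same start-date rules, followed by a safeguard: "If an imputed start date is later than the stop date, then the stop date (after any needed imputations) will be used instead" as the start. Neither Table 3 nor the rest of Section 9.1 has an equivalent.

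**Collection period.** Protocol Section 8.1: "All AEs are collected from the time the informed consent (and subject assent) is signed until the defined follow-up period". For the interval before dosing, Protocol Section 7.2.1.3 says "The 12 weeks between Screening and Randomization can be no less than 84 days and no more than 90 days". SAP Sections 1.3.1 and 2.1 also allow an 8-week baseline, depending on the protocol version that applied to the subject.

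**The concern.** Assigning an event of unknown timing to the treatment period is a normal conservative default. Table 3 also applies that default when the timing is known on the side that matters: a recorded stop date before the first dose shows that the event was over before any study drug. The rule then produces a record whose start is later than its stop, and the definition accepts it as treatment-emergent.

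Events that begin and end before dosing are to be expected, because collection starts at consent and at least 8 weeks of baseline follow. Each one caught by the rule adds to the treatment-emergent tables an event that treatment could not have caused. Those tables are also the main safety display in a trial of about 25 children, where one subject is a visible fraction of an arm.

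At the open-label boundary the effect is different. An event that ended in the double-blind phase can be moved out of the double-blind tables, which are the only placebo-controlled comparison, and into the open-label summary.

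**Working it through.** The documents give no figure on this point, so there is none to reproduce. The check applies the written rules to example records and then asks how often each missing-date pattern triggers the error.

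**1. One record through both tables.** Assumed dates: first dose 20 March 2020, event stop 10 March 2020 (complete).

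| Recorded start | Start under Table 3 | Treatment-emergent? | Start with the Table 2 check | Treatment-emergent? |
|---|---|---|---|---|
| wholly missing | 20 Mar 2020 | yes | 10 Mar 2020 | no |
| 2020 only | 20 Mar 2020 | yes | 10 Mar 2020 | no |
| March 2020 | 20 Mar 2020 | yes | 10 Mar 2020 | no |
| February 2020 | 1 Feb 2020 | no | 1 Feb 2020 | no |
| 2019 only | 1 Jan 2019 | no | 1 Jan 2019 | no |

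In the first three rows the imputed start is 10 days after the event ended. The last two rows are right without the check.

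**2. How often each pattern misclassifies.** Assumptions, none taken from the documents: first-dose dates spread evenly over the 366 days from 1 July 2019 to 30 June 2020; onset equally likely on each baseline day; event length *d* of 1 to 14 days; complete stop date. Only events that ended before the first dose are kept, which leaves *L* − *d* + 1 onset days per subject for a baseline of *L* days.

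- *Start wholly missing:* 100%, because the rule is unconditional.
- *Only the day missing:* the error needs onset in the calendar month of the first dose. For a first dose on day *k* of a month, that is *k* − *d* onset days (zero if negative). For *d* = 1 the sum over the 366 dates is 7×465 + 4×435 + 406 = 5,401, so the share is 5,401/(366×84) = 17.6%. For *d* = 14 the sum is 7×153 + 4×136 + 120 = 1,735, so the share is 1,735/(366×71) = 6.7%.
- *Only the year known:* the rule is right only if onset was in the previous calendar year. For *d* = 1 that is 84×85/2 = 3,570 of 30,744 combinations, so 1 − 3,570/30,744 = 88.4% are wrong. For *d* = 14 it is 14×71 + 70×71/2 = 3,479 of 25,986, so 86.6% are wrong.

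With an 8-week baseline (*L* = 56) the same formulas give:

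- day missing: 5,401/20,496 = 26.4% (*d* = 1) and 1,735/15,738 = 11.0% (*d* = 14);
- year only: 1 − 1,596/20,496 = 92.2% (*d* = 1) and 1 − 1,505/15,738 = 90.4% (*d* = 14).

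With the Table 2 check and a complete stop date, every share is 0%, because the start becomes a stop date that precedes the first dose. These are shares of events that already have the stated missing-date pattern. They say nothing about how common the pattern is.

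**3. The open-label branch.** Assume a placebo subject with first double-blind dose on 1 November 2019 and first open-label dose 17×7 = 119 days later, on 28 February 2020. An event has start 2020 only (or February 2020) and stop 10 February 2020. The known part does not match the first dose but matches the first open-label dose, so the start becomes 28 February 2020, 18 days after the event ended. Under Section 9.1 it leaves the double-blind tables and enters both the open-label summary and the whole-study summary of events after ganaxolone exposure, although it ended before the subject received ganaxolone. With the check the start is 10 February 2020 and the event stays in the double-blind phase.

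**4. Size per record.** About 25 subjects randomised 1:1 is about 12 per arm, and 1/12 = 8.3 percentage points. This is a maximum: Section 9.1 counts a subject once per preferred term, so incidence does not move if she already has that term on treatment. The event count rises by one either way.

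**The case against.** The strongest reply is that the triggering records should be rare. An event arising after consent would need a recorded stop but an unknown or matching partial start. Events are reviewed at Visits 1 and 2, Protocol Section 8.1.1 requires start and stop dates for each change in severity, and Protocol Section 9.2 provides for checks and queries on omissions. The listings show actual dates, so a pre-dose stop stays visible. Pre-dose events are also unrelated to allocation in expectation, so the error adds noise and over-counting rather than favouring one arm, and Section 9.1 plans no hypothesis test on adverse events. All of this stands and limits the size. It does not repair the rule, because no other passage compares start with stop.

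Some stronger readings are tempting, but the documents do not support them:

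- *Every partial start date is affected.* Rows four and five of the example show otherwise.
- *Every subject contributes at least 84 days before dosing.* The current text also provides for an 8-week baseline.
- *The event enters every treatment-emergent table, including the drug-related one.* Relatedness is the investigator's judgement under Protocol Section 8.1.2 and is not derived from the imputed date. An event that ended before dosing should normally be judged not related.
- *The event is tabulated in the randomised arm.* Safety tables use treatment actually received.

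The fix also has a limit. Table 3 imputes a partial stop to the end of the month or to 31 December, so an event whose stop is recorded only as the first-dose month or year will usually stay treatment-emergent. That is an acceptable default, because the timing is then unknown.

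**Conclusion.** The defect is real and follows from the text as written. For an event with a recorded pre-dose stop, Table 3 gives a start after the event ended, and hence a treatment-emergent label, in three patterns: start wholly missing, year only and equal to the first-dose year, or year and month equal to those of the first dose. The open-label branch can likewise move an event that ended in the double-blind phase into the open-label and ganaxolone-exposure summaries.

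The number of affected records cannot be derived from the documents and is probably small. Each one changes a preferred-term incidence by at most about 8 percentage points in the treatment-received group, assuming about 12 subjects per arm. The misclassification shares in the working depend on assumed dose dates, onset days, event lengths and complete stop dates; the example record depends only on the rules. The change should be made because the SAP already has the right rule for medications. This is not evidence of bias towards either arm.

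**What to change.** Add under SAP Table 3:

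- If the imputed start date is later than the stop date (after any needed imputation of the stop date), the stop date is used as the start date.
- An adverse event whose stop date is before the first dose of study drug is not treatment-emergent.
- The same comparison applies when the start has been imputed to the first open-label dose date, so that an event that ended before that dose is not assigned to the open-label phase.
- An event whose own stop date is partial and is imputed to on or after the first dose remains treatment-emergent by default.

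The cost is a few sentences in the SAP and about one line of derivation code. No new data are needed and no efficacy analysis changes. The sentences should be added before the double-blind database is locked.
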